5.2 Duration of Therapy

The protocol-specific therapy in this study is restricted to only 4 weekly doses of rituximab in patients randomized to the Rituximab-arm.

In the absence of treatment delays due to adverse event(s), treatment may continue for 4 weekly doses of Rituxaimab (or observation) or until one of the following criteria applies:

- Disease progression,
- Intercurrent illness that prevents further administration of treatment,
- Unacceptable adverse event(s),
- Patient decides to withdraw from the study, or
- General or specific changes in the patient's condition render the patient unacceptable for further treatment in the judgment of the investigator.

5.3 Duration of Follow Up

Patients will be followed for 4 weeks after removal from study or until death, whichever occurs first. Patients removed from study for unacceptable adverse event(s) will be followed until resolution or stabilization of the adverse event.

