This is a prospective randomized trial to test the efficacy of preemptive Rituxan in melanoma patients in reducing Immune-related adverse events (IRAEs) following combination checkpoint blockade (CCB). All eligible patients will undergo baseline evaluation to assess the status of disease as well as a baseline tumor biopsy. Combination checkpoint blockade will be administered as per current FDA approved standard of care, consisting of nivolumab at a dose of 1 mg/kg and ipilimumab at a dose of 3 mg/kg every 3 weeks for 4 doses, followed by nivolumab maintenance at a dose of 480 mg every 4 weeks x 1 year. Patients will be randomly assigned to no additional therapy (ARM A control) or 4 weekly doses of Rituxan for B cell depletion (ARM B). Rituxan will be administered as 375 mg/m2 IV for the first dose followed by weekly subcutaneous dosing at 1400 mg dose of Rituxan Hycela for weeks 2-4, as per recommended dosing for the FDA approval in the setting of lymphoma. All patients will be clinically monitored for the development of IRAEs utilizing NCI Common Toxicity Criteria v5.0. Any patient who received at least one dose of study drug will be included in safety analysis, and safety assessment will continue through treatment phase and up to 100 days after the last dose of study drug. Tumor response will be assessed according to the Response Evaluation Criteria in Solid Tumors (RECIST v1.1) and irRECIST at 12 weeks and every 12 weeks thereafter. All patients will also undergo pre treatment and post treatment biopsies if possible.

TABLE OF CONTENTS

SCH	EMA	3								
1.	OBJECTIVES	6								

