1.2 Secondary Objectives

- To evaluate the safety and tolerability (in terms of Rituxan-related adverse events) in patients with melanoma receiving CCB.
- To compare objective response rate in patients receiving CCB therapy + Rituxan versus CCB therapy alone.
- To compare 1 year overall and progression-free survival in patients receiving CCB therapy + Rituxan versus CCB therapy alone.
- To compare changes in CD21^{lo} B cells in patients receiving CCB therapy + Rituxan versus CCB therapy alone.
- To compare changes in T cells in patients receiving CCB therapy + Rituxan versus CCB therapy alone.

Exploratory Objectives

• To compare treatment induced changes in tumor tissue in patients receiving CCB therapy + Rituxan versus CCB therapy alone.

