5.4 Criteria for Removal from Study

Patients will be removed from study when any of the criteria listed in Section 5.2 applies. The reason for study removal and the date the patient was removed must be documented in the Case Report Form.

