14. STATISTICAL CONSIDERATIONS

14.1 Study Design/Endpoints

Endpoints:

Primary:

• Primary endpoint is the rate of CTC (v5.0) grade 3 or greater immune-related adverse events at 6 months of follow up.

Secondary:

- Rate of CTC (v5.0) toxicity related to Rituxan.
- Objective tumor response as assessed by RECIST v1.1 and irRECIST at 12 weeks and every 12 weeks thereafter.
- Rates of overall and progression-free survival at 1 year following initiation of therapy.

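### Read literally, Sections 5.2-5.4 end follow-up 4 weeks after disease progression, which conflicts with the 1-year overall survival endpoint and, for early progressors, with the 6-month IRAE endpoint

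*Combined protocol and SAP*

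**What the plan says.** Three consecutive sections set the rule.

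- Section 5.2 (Duration of Therapy): "treatment may continue for 4 weekly doses of Rituxaimab (or observation) or until one of the following criteria applies". Disease progression is the first criterion listed.
- Section 5.4: "Patients will be removed from study when any of the criteria listed in Section 5.2 applies".
- Section 5.3: "Patients will be followed for 4 weeks after removal from study or until death, whichever occurs first". The one exception is "Patients removed from study for unacceptable adverse event(s) will be followed until resolution or stabilization of the adverse event".

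The endpoints need longer observation.

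- Section 1.2 has the objective "To compare 1 year overall and progression-free survival in patients receiving CCB therapy + Rituxan versus CCB therapy alone", and Section 14.1 the endpoint "Rates of overall and progression-free survival at 1 year following initiation of therapy".
- Section 14.1 also states "Primary endpoint is the rate of CTC (v5.0) grade 3 or greater immune-related adverse events at 6 months of follow up".

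Other places give different or partial windows.

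- The Schema text says "safety assessment will continue through treatment phase and up to 100 days after the last dose of study drug".
- Section 7.2 closes adverse event reporting 30 days after the last study treatment or study discontinuation, whichever comes first. After that, only serious events attributed to study treatment are reported.
- Section 7.2 (Post-Study Adverse Events) asks for all deaths to be reported in studies that collect survival data.
- The first footnote to the table in Section 7.3.2 keeps expedited reporting for later serious events with at least possible attribution.
- Section 6 keeps patients who stop Rituxan for related grade 3 or greater toxicity in follow-up by intention to treat.
- Section 11 schedules CT scans every 12 weeks for two years, then less often.
- Section 12.1.4.3 asks for progression to be documented even after treatment stops for symptomatic deterioration.
- Section 14.2 plans Kaplan-Meier curves and Cox models.

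**The concern.** Taken together, 5.2, 5.4 and 5.3 tie the end of study follow-up to progression. Overall survival is the endpoint that most needs observation after progression. If staff follow 5.3 as written, vital status at 1 year is unknown for many patients who progressed, and censoring at that point is informative because those patients are at higher risk of death. The primary endpoint is reached too, but only for patients who progress early enough for the 4-week tail to end before 6 months.

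PFS is largely spared. Progression is itself the PFS event (Section 12.1.6), so removal at progression loses nothing. PFS is at risk only for patients removed without progression, for example for intercurrent illness or on the investigator's judgment.

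**Working it through.** **1. Timeline from the documents.** End of follow-up = week progression is found + 4. Six months is 26.1 weeks and one year 52.2 weeks.

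| Scan finding progression | Follow-up ends | Short of 6 months | Short of 1 year |
|---|---|---|---|
| Week 12 | Week 16 | 26.1 - 16 = 10.1 weeks | 52.2 - 16 = 36.2 weeks |
| Week 24 | Week 28 | none | 24.2 weeks |
| Week 36 | Week 40 | none | 12.2 weeks |
| Week 48 | Week 52 | none | about one day (336 + 28 = day 364) |

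The IRAE window is cut for progression found before week 26.1 - 4 = 22.1, which at scheduled scans means week 12.

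**2. Do the safety windows fill the gap?** Six months is about day 183. Counting 100 days from the calendar's week-5 Rituxan dose gives 29 + 100 = day 129. Counting from the week-10 ipilimumab/nivolumab dose gives 64 + 100 = day 164. Both fall short. The 30-day window from the week-5 dose ends at 29 + 30 = day 59.

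**3. Size for overall survival (assumed inputs).** The documents give no progression or post-progression survival rates. Assumed: 1-year PFS 35%, 45% or 55%; post-progression median 6, 9 or 12 months; death without progression 0.005 per month; exponential times; scans every 84 days. Progression hazard = -ln(PFS)/12 - 0.005, which is 0.0825 per month at 35% and 0.0448 at 55%. Post-progression hazard = ln 2 / median. Simulating 400,000 patients for each of the nine combinations gives:

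- Alive when follow-up ends before 1 year: 29-51% of all patients. Leaving out those found at week 48, who lose about one day: 23-42%, or 0.23 x 44 = 10 to 0.42 x 44 = 18.5, so 10-19 of 44.
- Kaplan-Meier minus true 1-year OS if deaths after the 4 weeks are not captured: +6.0 to +13.4 points.
- The same difference if all deaths are captured but survivors are censored at 4 weeks (analysis at 1 year): -2.0 to -6.4 points.

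For scale, the 95% half-width for an OS difference with complete follow-up is 1.96 x sqrt(2p(1-p)/22) = 29, 27 and 24 points at p = 0.6, 0.7 and 0.8.

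**4. Size for the primary endpoint.** Section 14.2's figure first: exact power of the one-sided 0.05 Fisher test, 22 per arm, 60% v 20%, is 79.1%, agreeing with the stated 80%.

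The share with the window cut at week 16 is 9-18% (4-8 of 44) in the same simulation. A closed form confirms the ends. It integrates progression before 84 days (2.76 months) with survival to 112 days (3.68 months):

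- PFS 35%, median 12 months: 0.0825 x exp(-0.0578 x 3.68) x [1 - exp(-0.0297 x 2.76)]/0.0297 = 0.177.
- PFS 55%, median 6 months: 0.0448 x exp(-0.1155 x 3.68) x [exp(0.0657 x 2.76) - 1]/0.0657 = 0.089.

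No section says how an incomplete window is scored. Suppose 10-25% of these patients' IRAEs start after week 16 (assumed) and count as no event. Observed rate = true rate x (1 - share cut x late share):

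- 9% and 10%: 0.60 x 0.991 = 59.5% v 19.8%, power 78.4%.
- 18% and 25%: 0.60 x 0.955 = 57.3% v 19.1%, power 75.7%.

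If such patients were excluded instead, 20 or 18 per arm would give 75.3% or 74.2%.

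**The case against.** The best defence is that the list in 5.2 sits under a therapy heading, in a section that limits protocol therapy to four weekly rituximab doses. By week 12 that therapy is over, so progression found then need not trigger removal. On this reading the list applies only during weekly dosing, and with 12-week scans essentially no one is removed for scan-detected progression. Only progression recognised clinically before a scan could matter. The documents give no rate for that, so no bias figure can be attached to this reading.

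The wider text supports an intention to follow patients longer: years of scans, planned survival curves, death reporting after the adverse event period, intention-to-treat follow-up after Rituxan toxicity, and effort to document progression after discontinuation.

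Much of this stands. It makes the point a contradiction to reconcile, and it does not show that survival data will go uncollected. It does not remove the point. Section 5.4 reuses the 5.2 list as grounds for leaving the study and sets no time limit. The death-reporting text has no contact schedule, end date or last-known-alive date. The late serious-event reporting depends on attribution. The Section 6 provision covers one reason for stopping only. None of these mentions or overrides 5.3, and staff could reasonably apply either reading.

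**Conclusion.** The conflict is in the wording and needs no assumption: about week 16 under 5.2-5.4, against 26 and 52 weeks under 14.1. It should be fixed, chiefly for 1-year OS. The percentages and bias figures apply to the broad reading only and rest on the assumed progression, survival and late-onset rates. The direction of the OS bias depends on which sections staff follow.

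A reader might infer more than the documents support:

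- That the survival comparison between arms is biased. No difference in loss by arm is shown, and OS is an unpowered, descriptive comparison whose confidence interval half-width (24-29 points) exceeds the bias.
- That the primary analysis is seriously compromised. The modelled power loss is 1-3 points if missed events count as none, and about 4-5 points if the patients are excluded.
- That a missed late IRAE would be scored as no event. Section 12.1.1 says only from when patients are evaluable for toxicity; it is silent on incomplete windows.

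**What to change.** Reconcile Sections 5.2-5.4 with the Schema text, the adverse event reporting period and post-study text in 7.2, the calendar in Section 11, and Sections 1.2 and 14.1, by separating end of protocol treatment from end of study follow-up. State in 5.3 that, unless consent is withdrawn:

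1. vital status and last-known-alive date are collected by chart or telephone for all patients to at least 12 months from start of therapy;
2. grade 3 or greater IRAEs are collected to 6 months regardless of progression or stopping treatment, with the reporting period in 7.2 aligned to this;
3. for patients who stop without progression, the scans already in the calendar are used until progression.

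The cost is rewording a few sections and a small number of added status and IRAE checks for at most 44 patients. No dose, treatment rule or scan schedule changes.

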5.4 Criteria for Removal from Study

Patients will be removed from study when any of the criteria listed in Section 5.2 applies. The reason for study removal and the date the patient was removed must be documented in the Case Report Form.

6. DOSING DELAYS/DOSE MODIFICATIONS

There is no dose modification for Rituxan in this study. Patients who experience Rituxan-related grade 3 or greater toxicity will not receive further Rituxan, and will be followed on the Rituxan-arm on an intent to treat basis.

Management of Ipilimumab and Nivolumab therapy in this protocol will be as per FDA approved standard of care guidelines and per the discretion of the treating investigator.

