2.2 IND Agent(s)

Rituxan Hycela

Rituxan Hycela is a combination of rituximab, a CD20-directed cytolytic antibody, and hyaluronidase human, an endoglycosidase, indicated for the treatment of adult patients with Follicular Lymphoma (FL), Diffuse Large B-cell Lymphoma (DLBCL), and Chronic Lymphocytic Leukemia (CLL). Rituxan has also been extensively utilized for therapy of autoimmune disorders such as immune thrombocytopenic purpura. The proposed use of Rituxan in this study is based on new data from the PI regarding the role of CD21^{lo}CD20⁺ B cells in the pathogenesis of immune related adverse events following combination checkpoint blockade.

Please note Rituxan Hycela is always given as Rituximab IV as the first dose, if no reaction can proceed to Rituxan Hycela.

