5. TREATMENT PLAN

5.1 Agent Administration

Once the investigator has signed the eligibility checklist, randomization may proceed. Patients meeting study entry criteria will be randomized to treatment ARM A or Arm B by the study statistician, [name]. Eligible subjects (eligibility confirmed and checklist signed) will be assigned to a treatment arm until 44 subjects (22 in each arm) have been enrolled. The study coordinator will update Oncore and ERMS reflect randomization information.

Following randomization, patients should begin protocol treatment within 5 business days. Issues that would cause treatment delays should be discussed with the Principal Investigator.

Treatment will be administered on an *outpatient* basis. Reported adverse events and potential risks are described in Section 7. Appropriate dose modifications are described in Section 6. No investigational or commercial agents or therapies other than those described below may be administered with the intent to treat the patient's malignancy.

Patients will be randomly assigned 1:1 using block randomization with a block of 6 patients. Randomization schema will be kept in the research pharmacy.

Patients with unresectable stage III or stage IV melanoma being treated with FDA approved standard of care immune checkpoint combination therapy with Ipilimumab and Nivolumab are eligible for this trial.

Patients will be randomized 1:1 to either continue therapy with standard of care Ipilimumab and Nivolumab (ARM A) or standard of care Ipilimumab and Nivolumab plus **4 doses of weekly Rituxan** (ARM B).

Patients enrolling on this study following treatment failure on single agent anti-PD-1 will be distributed equally between arms A and B of the study.

Induction Phase:

ARM A: Cycles 1-4

Each cycle is 21 days and includes Ipilimumab (3 mg/kg) on day 1 plus Nivolumab (1 mg/kg) on Day 1.

ARM B. Cycles 1-4

Each cycle is 21 days and includes Ipilimumab (3 mg/kg) on day 1 plus Nivolumab (1 mg/kg) on

Version Date: 04-05-2021 v6.0

Day 1. In addition, patients will receive 4 weekly doses of Rituxan (first dose 375 mg/m2 IV and then 3 weekly doses of 1400 mg Rituxan Hycela subcutaneous, as per current label for Rituxan Hycela).

First dose of Rituxan will be administered 1 week after start of Ipi/Nivolumab therapy. 3rd dose of Rituxan will be administered on day 2 of cycle 2 after infusion of Ipi/Nivo on week4.

Continuation Phase:

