starting treatment with RITUXAN HYCELA. If patients are not able to receive one full dose by intravenous infusion, they should continue subsequent cycles with a rituximab product by intravenous infusion and not switch to RITUXAN HYCELA until a full intravenous dose is successfully administered. Refer to the prescribing information for a rituximab product for intravenous infusion for additional information (Rituxan prescribing information, Genentech).

Premedicate approximately 30 minutes before each dose of RITUXAN HYCELA. Dose reductions of RITUXAN HYCELA are not recommended. The recommended dose is RITUXAN HYCELA 1,400 mg/23,400 Units (1,400 mg rituximab and 23,400 Units hyaluronidase human) subcutaneously at a fixed dose irrespective of patient's body surface area. The dosing for Rituxan Hycela utilized in this protocol is similar to that FDA approved for follicular lymphoma.

Recommended Premedication and Prophylactic Medications: Premedicate with acetaminophen and an antihistamine before each dose of RITUXAN HYCELA.

Administration and Storage

RITUXAN HYCELA is ready to use. To avoid needle clogging, attach the hypodermic injection needle to the syringe immediately prior to administration. RITUXAN HYCELA is compatible with polypropylene and polycarbonate syringe material and stainless steel transfer and injection needles. Use the product immediately. Parenteral drug products should be inspected visually for particulate matter and discoloration prior to administration. RITUXAN HYCELA should be a clear to opalescent and colorless to yellowish liquid. Do not use vial if particulates or discoloration is present.

Administration

- Inject RITUXAN HYCELA into the subcutaneous tissue of the abdomen over approximately 5–7 minutes and never inject into areas where the skin is red, bruised, tender or hard, or areas where there are moles or scars. No data are available on performing the injection at other sites of the body.
- Inject 11.7 mL of RITUXAN HYCELA 1,400 mg/23,400 Units vial (1,400 mg rituximab and 23,400 Units hyaluronidase human) subcutaneously into the abdomen over approximately 5 minutes.

If administration of RITUXAN HYCELA is interrupted, continue administering at the same site, or at a different site, but restricted to the abdomen.

During treatment with RITUXAN HYCELA, do not administer other medications for subcutaneous use at the same sites as RITUXAN HYCELA.

Storage:

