
Local Cutaneous Reactions

Local cutaneous reactions, including injection site reactions, have been reported in patients receiving RITUXAN HYCELA. Symptoms included pain, swelling, induration, hemorrhage, erythema, pruritus, and rash. Some local cutaneous reactions occurred more than 24 hours after RITUXAN HYCELA administration. The incidence of local cutaneous reactions following administration of RITUXAN HYCELA was 16%. Reactions were mild or moderate and resolved without any specific treatment. Local cutaneous reactions of any Grade were most common during the first RITUXAN HYCELA cycle (Cycle 2; 5%) with the incidence decreasing with subsequent injections.

Tumor Lysis Syndrome (TLS)

TLS can occur within 12–24 hours after administration of a rituximab-containing product, including RITUXAN HYCELA. A high number of circulating malignant cells (≥ 25,000/mm3) or high tumor burden confers a greater risk of TLS. Administer aggressive intravenous hydration and anti-hyperuricemic therapy in patients at high risk for TLS. Correct electrolyte abnormalities, monitor renal function and fluid balance, and administer supportive care, including dialysis as indicated.

Infections

Serious, including fatal, bacterial, fungal, and new or reactivated viral infections can occur during and following the completion of therapy with rituximab-containing products, including RITUXAN HYCELA. The incidence of infections with RITUXAN HYCELA vs rituximab was 56% and 49% respectively in patients with CLL, and 46% and 41% respectively in patients with FL/DLBCL in combination with chemotherapy. Infections have been reported in some patients with prolonged hypogammaglobulinemia (defined as hypogammaglobulinemia > 11 months after rituximab exposure). New or reactivated viral infections included cytomegalovirus, herpes simplex virus, parvovirus B19, varicella zoster virus, West Nile virus, and hepatitis B and C. Discontinue RITUXAN HYCELA for serious infections and institute appropriate anti-infective therapy.

Cardiovascular Adverse Reactions

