Cardiac adverse reactions, including ventricular fibrillation, myocardial infarction, and cardiogenic shock may occur with rituximab-containing products, including RITUXAN HYCELA. Discontinue RITUXAN HYCELA for serious or life threatening cardiac arrhythmias. Perform cardiac monitoring during and after all administrations of RITUXAN HYCELA for patients who develop clinically significant arrhythmias, or who have a history of arrhythmia or angina.

Renal Toxicity

Severe, including fatal, renal toxicity can occur after administration of rituximab-containing products, including RITUXAN HYCELA. Renal toxicity has occurred in patients who experience tumor lysis syndrome and in patients with administered concomitant cisplatin therapy during clinical trials. The combination of cisplatin and RITUXAN HYCELA is not an approved treatment regimen. Monitor closely for signs of renal failure and discontinue RITUXAN HYCELA in patients with a rising serum creatinine or oliguria.

Bowel Obstruction and Perforation

Abdominal pain, bowel obstruction and perforation, in some cases leading to death, can occur in patients receiving rituximab-containing products, including RITUXAN HYCELA, in combination with chemotherapy. In postmarketing reports, the mean time to documented gastrointestinal perforation was 6 (range 1–77) days. Evaluate if symptoms of obstruction such as abdominal pain or repeated vomiting occur.

Immunization The safety of immunization with live viral vaccines following rituximabcontaining products, including RITUXAN HYCELA, therapy has not been studied and vaccination with live virus vaccines is not recommended before or during treatment.

Embryo-Fetal Toxicity

Based on human data, rituximab-containing products can cause fetal harm due to B-cell lymphocytopenia in infants exposed to rituximab in-utero. Advise pregnant women of the risk to a fetus. Females of childbearing potential should use effective contraception while receiving RITUXAN HYCELA and for 12 months following the last dose of rituximab-containing products, including RITUXAN HYCELA.

Immunogenicity

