9.1 Investigational Agent(s)

Rituxan Hycela:

Mechanism of Action

Rituximab is a monoclonal antibody that targets the CD20 antigen expressed on the surface of pre-B and mature B-lymphocytes. Upon binding to CD20, rituximab mediates B-cell lysis. Possible mechanisms of cell lysis include complement dependent cytotoxicity (CDC) and antibody dependent cell mediated cytotoxicity (ADCC). Hyaluronan is a polysaccharide found in the extracellular matrix of the subcutaneous tissue. It is depolymerized by the naturally occurring enzyme hyaluronidase. Unlike the stable structural components of the interstitial matrix, hyaluronan has a half-life of approximately 0.5 days. Hyaluronidase human increases permeability of the subcutaneous tissue by temporarily depolymerizing hyaluronan. In the doses administered, hyaluronidase human in RITUXAN HYCELA acts locally.

The effects of hyaluronidase human are reversible and permeability of the subcutaneous tissue is restored within 24 to 48 hours.

Version Date: 04-05-2021 v6.0

Hyaluronidase human has been shown to increase the absorption rate of a rituximab product into the systemic circulation when given in the subcutis of Göttingen Minipigs.

Rituxan Hycela is given IV Rituximab as first dose followed by rituxan hycela subcutaneously for subsequent doses for those without severe infusion reactions.

DESCRIPTION

RITUXAN HYCELA is a combination of rituximab and hyaluronidase human. Rituximab is a genetically engineered chimeric murine/human monoclonal IgG1 kappa antibody directed against the CD20 antigen. Rituximab has an approximate molecular weight of 145 kD. Rituximab has a binding affinity for the CD20 antigen of approximately 8.0 nM. Rituximab is produced by mammalian cell (Chinese Hamster Ovary) suspension culture in a nutrient medium that may contain the antibiotic gentamicin. Gentamicin is not detectable in the final product. Recombinant human hyaluronidase is an endoglycosidase used to increase the dispersion and absorption of co-administered drugs when administered subcutaneously. It is produced by mammalian (Chinese Hamster Ovary) cells containing a DNA plasmid encoding for a soluble fragment of human hyaluronidase (PH20). It is a glycosylated single-chain protein with an approximate molecular weight of 61 kD.

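### After a reaction to the first IV Rituxan dose, the protocol gives opposite instructions on continuing Rituxan and two different bars for switching to subcutaneous dosing

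*Combined protocol and SAP*

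**What the plan says.** Arm B is planned as four weekly Rituxan doses: "first dose 375 mg/m2 IV and then 3 weekly doses of 1400 mg Rituxan Hycela subcutaneous" (Section 5.1). Four other places bear on what happens after the first dose.

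- **Section 6** opens with "There is no dose modification for Rituxan in this study" and continues: "Patients who experience Rituxan-related grade 3 or greater toxicity will not receive further Rituxan". Such patients stay in follow-up on their arm by intent to treat.
- **Section 5.1.1** (Rituxan Hycela) requires one complete IV dose, tolerated without a severe reaction, before subcutaneous treatment starts. Of patients who could not be given a complete IV dose it says "they should continue subsequent cycles with a rituximab product by intravenous infusion and not switch to RITUXAN HYCELA" until one has been given.
- **Section 2.2** says the product is "always given as Rituximab IV as the first dose, if no reaction can proceed to Rituxan Hycela".
- **Section 9.1** describes IV rituximab first, "followed by rituxan hycela subcutaneously for subsequent doses for those without severe infusion reactions".

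Section 5.1 also sends the reader to Section 6 for dose changes and to Section 7 for risks. Section 5.2 lists general reasons to end the weekly doses, including unacceptable adverse events and the investigator's judgment.

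**The concern.** Rituxan is the only protocol-specific therapy in the trial (Section 5.2), and the first infusion is where a reaction is most expected: Section 7.1 gives that as the reason for starting with the IV form, and notes that fatal infusion reactions have been reported. The instructions for the next dose should therefore lead any two physicians to the same action.

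They do not. Two physicians treating the same patient could act in opposite ways, one stopping and one re-exposing after a grade 3 or greater reaction, and each could cite the protocol. What is at stake is patient safety first, and then a consistent definition of the Arm B intervention.

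**Working it through.** The check is a comparison of texts. Each situation after dose 1 is set against each section.

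| Situation after the first IV dose | Section 6 | Section 5.1.1 | Section 2.2 | Section 9.1 | Section 5.1 schedule |
|---|---|---|---|---|---|
| 1. Rituxan-related grade 3 or greater reaction, infusion not completed | No further Rituxan | Continue IV rituximab; no switch until a full IV dose is given | No switch | No switch if the reaction is severe | Subcutaneous only for doses 2 to 4 |
| 2. Non-severe reaction, infusion completed | No stop triggered | Switch allowed | Switch not allowed | Switch allowed | Subcutaneous only for doses 2 to 4 |

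**Situation 1.** The trigger in Section 6 is grade plus attribution. The trigger in Section 5.1.1 is failure to complete the infusion, whatever the reason. A grade 3 or greater reaction that ends the infusion early satisfies both. Section 6 then ends Rituxan by any route, and Section 5.1.1 directs more of it by vein. The two cannot both be followed. The Section 5.1 schedule does not help, because it plans only subcutaneous doses after the first and so has no place for the continued IV dosing that Section 5.1.1 describes.

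**Situation 2.** Section 2.2 makes the switch conditional on there being no reaction, with no grade attached. Sections 5.1.1 and 9.1 attach the condition to severe reactions only. A patient with a mild reaction and a completed infusion may switch under two sections and may not under the third. Section 2.2 does not say what such a patient receives instead.

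**Precedence.** No section ranks these texts. The pointer from Section 5.1 to Section 6 says where dose changes are described. It does not say that Section 6 overrides Section 5.1.1, and Section 6 is silent on incomplete infusions, reactions below grade 3 and route.

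**The plan's own figure.** Section 14.2 states about 80% power for 22 per arm, 60% versus 20%, with Fisher's exact test at one-sided 0.05. Exact power is the sum, over all pairs (x, y), of Bin(x; 22, 0.60) × Bin(y; 22, 0.20), counting only pairs with a one-sided Fisher p-value of at most 0.05. The result is 79.1%, which agrees with the plan. The point here does not touch that figure.

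**The case against.** The strongest reply is that the texts can be read together. Section 5.1.1 reads like product labelling. It even speaks of cycles, although Rituxan is given weekly here and the protocol's cycles are 21 days. Section 6 is specific to this study, and Section 5.1 names it for dose changes. On that reading, Section 5.1.1 covers incomplete infusions below grade 3, Section 6 covers the rest, and Section 2.2 is one loose background phrase about route. Section 5.2 also lets the investigator stop for an unacceptable event, and intent to treat protects the randomized comparison.

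This reading is plausible, and it shows how narrow situation 1 is. But the reader has to supply it. Section 5.1.1 sits in the Treatment Plan, is worded as an instruction and carries no exception for grade. Intent to treat settles where a patient is analysed, not whether the next dose is given. Section 5.2 permits stopping but does not remove the instruction to continue.

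Four stronger readings may tempt a reader, and the documents do not support them.

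- *Section 7.1 contradicts Section 6 on other toxicities.* Section 7.1 says to "discontinue RITUXAN HYCELA in patients with a rising serum creatinine or oliguria", and also "Discontinue RITUXAN HYCELA for serious infections and institute appropriate anti-infective therapy", without reference to attribution. Section 6 does not say that Rituxan stops only for related grade 3 or greater toxicity, so following Section 7.1 breaks nothing in Section 6.
- *These are the only stopping rules.* Section 5.2 has others.
- *Every affected patient receives either one dose or four.* In situation 2, Section 2.2 restricts the product switch and does not say that rituximab ends. In situation 1, the first dose is itself incomplete.
- *Power falls by a stated amount.* That needs a reaction rate, which the documents do not give, and an assumption that a single IV dose has no benefit.

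**Conclusion.** The protocol is wrong as written in two places. Section 6 and Section 5.1.1 give opposite instructions for a first infusion cut short by a Rituxan-related grade 3 or greater reaction. Section 2.2 conflicts with Sections 5.1.1 and 9.1 on whether a non-severe reaction bars the subcutaneous switch. The first is the more serious, because it concerns re-exposure after a severe reaction, and it would justify the correction alone.

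The reach is limited to Arm B (22 patients planned), and within it to those who react to the first dose. How many that is cannot be derived from the documents. The conclusion rests on the wording alone and on the absence of any precedence clause. It assumes no reaction rate and no loss of benefit, and it takes no view on which clinical rule is right.

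**What to change.** The sponsor and the drug supplier should reconcile Sections 2.2, 5.1, 5.1.1, 6 and 9.1 into one statement in Section 6. For each combination of reaction grade and first infusion completed or not, it should say whether further Rituxan is given and by which route. Severe should be tied to a grade, so that the switching rule and the stopping rule use the same scale. The other sections should then refer to Section 6 in place of their own wording, and the Section 5.1 schedule should match whatever routes are allowed. The content of each rule is for the sponsor and supplier to settle.

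The cost is one text amendment, with no added patients, visits or tests and no change to the sample size.
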